Endpoints	Primary endpoints:  Extent of agreement between Bloomlife MFM-Pro and CTG in fetal heart rate (FHR) and maternal heart rate (MHR):  95% LoA for FHR within +/- 10 bpm  95% LoA for MHR within +/- 7 bpm  Regression analysis of MFM-Pro vs CTG for fetal heart rate and maternal heart rate determining if the bias is constant across the range of the measurements.  Secondary endpoints:  Summary tables of recorded adverse events, serious adverse events, adverse device effects, device deficiencies.  Exploratory endpoints:  Percentage of a recording with a FHR for Bloomlife MFM-Pro and for CTG.  Percentage of a recording with a MHR for Bloomlife MFM-Pro and for CTG.  Sensitivity and False Event Rate for uterine contractions annotated by experts based on uterine activity traces measured with Bloomlife MFM-Pro and with CTG.

	
 
Confusion matrix between the signal quality check result (pass or fail) and the recording quality (for the MFM-Pro fetal heart rate signal, over the complete measurement)
 

Design	National, prospective, cross-sectional, interventional, single-arm study.
Number of subjects	Pilot phase: up to 200 enrolled subjects Pivotal phase: up to 60 enrolled subjects
Inclusion criteria	
 
Pregnant woman ≥ 18 years old
 
Gestational age ≥ 32 weeks and 0 days
 
Singleton pregnancy
 
Ability to read and understand English or Spanish
 
Willingness to participate in the study
 

Exclusion criteria	
 
Implanted pacemaker or any other implanted electrical device
 
Plurality higher than 1
 
History of allergies to skin adhesives
 
Irritated or lesioned skin at the Bloomlife MFM-Pro electrodes locations
 
Contraindication to the use of CTG (e.g. due to preterm contractions)
 

Enrolment criteria	A participant is considered enrolled when their eligibility is confirmed, and the signal validation screening test (performed by the Bloomlife MFM-Pro) gives a successful result.
Study duration	Q1 2021 – Q2 2022
Study Procedures	Informed consent: Eligible participants will be asked to sign an informed consent form before any study-specific procedure is performed.  MFM-Pro electrodes connection check & signal quality check: Once the informed consent is signed, participants are asked to sit on a reclined (NST) chair (or lie on a hospital bed).

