	The researcher prepares the patient's skin by cleaning it and by using medical skin-prep tape on her belly.  The researcher proceeds with setting up the Bloomlife MFM-Pro system, in parallel with the CTG. The researcher instructs the participant to annotate perceived contractions by pressing a button.
	With this setup, data is collected with both devices, while the Bloomlife MFM-Pro performs an electrode connection check and signal quality check (screening test). This step may take up to 15 minutes. If the electrode connection check fails or the CTG does not capture the MHR/FHR signals, the measurement setup is adjusted as needed (up to three attempts are allowed).
	Study measurement:  If the electrodes connection check and the CTG setup are successful, data is collected with both the Bloomlife MFM-Pro and the CTG monitor for 45 minutes.
	A video of the belly and a picture of the setup may also be taken.
	During the data collection, the researcher uses a custom data visualization interface to visualize data from the CTG and the Bloomlife MFM-Pro, to identify issues with the measurement setup and annotate relevant events in the data collection process.
	At the end of the data collection, the Bloomlife MFM-Pro and CTG tracings are stored in a digital format for analysis.
	After the Bloomlife MFM-Pro data collection, relevant information pertaining to the subject's pregnancy and medical history is collected from her medical records and entered in the eCRF.
	Any adverse event observed during the data collection (signal quality check and measurement) will be recorded by the researcher. Information about other adverse events will be collected from the participant's medical records for 7 days after the measurement.
Statistical Data	Limits of Agreement:
Analysis	For assessing the agreement between the Bloomlife MFM-Pro fetal heart rate (FHR) and a standard of care

	Cardiotocograph (CTG), we plan to estimate the 95% limits of agreement (LoA) according to Bland-Altman, together with 95% confidence intervals (95%CI).
	
 
95% limits of agreement objectives:
 
1. Fetal heart rate the 95% limits of agreement lie within +/- 10 bpm
 
2. Maternal heart rate the 95% limits of agreement lie within +/- 7 bpm.
 

	Linear regression analysis:
	A linear regression analysis assessing the relationship between the bias and the magnitude of measurements will also be performed.

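### The confidence intervals planned for the limits of agreement are valid only for near-normal differences, and the plan gives no check or alternative

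*Combined protocol and SAP*

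**What the plan says.** The Limits of Agreement paragraph under Statistical Data Analysis (Clinical Investigation Plan Summary) names one method: "we plan to estimate the 95% limits of agreement (LoA) according to Bland-Altman, together with 95% confidence intervals (95%CI"). That sentence refers to FHR; the objectives listed under it cover both rates: "Fetal heart rate the 95% limits of agreement lie within +/- 10 bpm" and "Maternal heart rate the 95% limits of agreement lie within +/- 7 bpm". The primary endpoints repeat the criteria: "95% LoA for FHR within +/- 10 bpm" and "95% LoA for MHR within +/- 7 bpm".

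The design elements that matter here are "Pivotal phase: up to 60 enrolled subjects" and, for each woman, "data is collected with both the Bloomlife MFM-Pro and the CTG monitor for 45 minutes". The only other planned analysis of the differences is a linear regression of bias on magnitude.

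The summary does not state:
- which variant of Bland-Altman is meant;
- the pairing interval or the unit of analysis;
- a check of the distribution, or a rule for outliers or artefacts;
- whether the point limits or their confidence intervals must lie inside the margins.

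**The concern.** The usual Bland-Altman interval takes its width from the sampling variance of an SD under normality. If the differences are a narrow core plus a small share of larger errors, the SD depends heavily on those errors. It then varies from trial to trial far more than the formula allows, so the reported interval gives false precision around the figure on which equivalence is judged. Mean ± 1.96 SD may also stop marking the central 95% of pairs, and the comparison with ±10 or ±7 bpm then answers a different question from the one a reader expects. Regressing bias on magnitude looks for a trend and would not reveal heavy tails. The problem remains even if all pairs are independent, so it is separate from the question of repeated pairs within a woman.

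**Working it through.** The documents give no SD, error rate or sample-size calculation, so there is no figure of the plan's to reproduce.

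**Inputs.** From the plan: margins ±10 bpm (FHR) and ±7 bpm (MHR), up to 60 women, 45 minutes each. Assumed: a normal core with SD 3 bpm (FHR) or 2 bpm (MHR) unless stated, plus a share p of pairs displaced by G bpm. Where many pairs are needed, one pair per minute is assumed: 60 × 45 = 2,700.

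**Normal baseline.** Limits are mean ± 1.96 SD, with SE = SD × √(1/n + 1.96²/(2(n−1))). At zero bias the point limits pass if SD ≤ 10/1.96 = 5.10 (FHR) or 7/1.96 = 3.57 (MHR). With n = 60 the interval half-width is 2.00 × √(1/60 + 3.84/118) = 0.44 SD, and simulated coverage is 94.7%. The method works when the differences are normal.

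**Interval width, symmetric errors.** With kurtosis k, the true SE exceeds the formula by √[(1 + 0.9604(k−1)) / 2.921], where 0.9604 = 1.96²/4 and 2.921 = 1 + 1.96²/2.
- FHR, 1% at ±60: k = 65.1, ratio √(62.6/2.921) = 4.6.
- MHR, 1% at ±60: k = 81.6, ratio 5.2.
- FHR, 6% at ±15: k = 7.92, ratio √(7.65/2.921) = 1.6.
- Core SD 2, 15.3% at ±12: k = 5.53, ratio √(5.35/2.921) = 1.35.

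**Coverage of the nominal 95% interval.** In large samples this is about 2Φ(1.96/ratio) − 1. The 6% at ±15 case gives 2Φ(1.21) − 1 = 77%, and the 15.3% at ±12 case gives 2Φ(1.45) − 1 = 85%. For one-sided errors the skewness γ adds 1.96|γ| to the numerator for the limit on the error side. With 1% at −60 (core SD 3), k = 63.6 and γ = −7.03, so the ratio is √[(1 + 60.1 + 13.8)/2.921] = 5.06 and coverage is 30%.

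| Setting (simulated) | Coverage |
|---|---|
| n = 60, 1% at ±60 | 21% (FHR), 18% (MHR) |
| n = 60, 6% at ±12 to ±15 | 69–82% |
| 60 women × 45 pairs, 0.5–1% at −60 | 14–26% |
| 60 women × 45 pairs, 6% at ±15, mixtures tried | 40–76% |
| Those 60 × 45 mixtures, whole-woman bootstrap around mean ± 1.96 SD | 89–96% |

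**Towards a fail.** With ±60 bpm errors the limits leave the margin once p exceeds (5.102² − 9)/3600 = 0.47% (FHR) or (3.571² − 4)/3600 = 0.24% (MHR). At p = 1% the FHR limits are ±1.96√(9 + 36) = ±13.1, while the true 2.5th and 97.5th percentiles are about ±6.1. For MHR the figures are ±12.4 against ±4.1.

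**Towards a pass.**
- FHR, 6% at ±15: limits ±1.96√(9 + 13.5) = ±9.3, a pass. The share outside 10 bpm is 0.06 × Φ(5/3) + 0.94 × 0.0009 = 5.8%, and the true percentiles are ±12.1.
- MHR, 6% at ±12: limits ±1.96√(4 + 8.64) = ±6.97, a pass. The share outside 7 bpm is 0.06 × Φ(2.5) + 0.94 × 0.0005 = 6.0%.
- MHR, 3% one-sided at −15: the lower limit is −6.8 and the true 2.5th percentile is −13.1. Only about 3% of pairs lie outside, but all in one tail.

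The largest error for which this can happen is about 18 bpm (FHR) or 13 bpm (MHR) at a 5% symmetric rate, and about 24 or 17 bpm at a 2.5% one-sided rate.

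**Dependence on pairing.** Take core SD 3 and one-sided −60 bpm errors. If each second is a pair, 0.438% of 45 minutes (0.00438 × 2,700 s = 11.8 s) puts the lower limit at −10. With one-minute averages the same 11.8 s moves one value in 45 by 60 × 11.8/60 = 11.8 bpm. The mean is −0.26, the SD is √(9 + 11.8² × (1/45)(44/45)) = 3.47, and the limits are −7.1 and +6.5, well inside.

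**The case against.** The strongest reply is that the premise is not in the documents. They report no distribution and no error rate, and the formula is inferred from the name of the method. The text is a summary, so missing detail is weak evidence of a wrong method. Enrolment requires that "the signal validation screening test (performed by the Bloomlife MFM-Pro) gives a successful result", setup may be adjusted, and traces are watched live. The exploratory endpoint on the percentage of recording with a heart rate suggests that poor signal may give missing values rather than wrong ones. All of this bears on how common errors would be and stands as a reason for caution about size. None of it is an analysis rule for the differences.

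A reader might infer that occasional gross errors can turn the verdict either way. They cannot: at the population level, errors of 60 bpm push only towards a fail, and a misleading pass needs errors of roughly 12–24 bpm. A reader might also infer that a few seconds of artefact would fail the device. That holds with second-by-second pairs and disappears with one-minute averages. If each woman contributed a single mean, 1% of one-sided 60 bpm errors would move it by only 0.6 bpm, and the problem would largely vanish unless errors gathered in a few women.

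Nor do these results require percentile limits as the primary criterion. With core SD 2 and 2.4% of pairs at each of +60 and −60 bpm, percentile limits are about ±6.2 and pass, although 4.8% of pairs are wrong by 60 bpm. Mean ± 1.96 SD gives ±1.96√(4 + 0.048 × 3600) = ±26. Penalising such errors may well be wanted in a fetal monitor.

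**Conclusion.** The concern holds in a limited form. The plan names a method whose standard intervals depend on near-normal differences, and it supplies no check and no alternative. If the differences contain a small share of larger errors, the intervals are too narrow. The true SE is about 4–7 times the formula for rare 60 bpm errors (coverage roughly 15–30%). It is about 1.4–1.9 times for moderate symmetric ones (coverage roughly 70–85% when errors are independent). So it would be wrong to call the intervals far too narrow in general.

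The limits can also misdescribe the central 95% of pairs, in a direction set by error size. More than 5% of pairs outside the margin together with a pass was shown for two-sided errors of about 12–18 bpm. At the one-sided extreme of about 24 bpm, a tail percentile lies outside the margin but the total share outside is nearer 2.5–3%.

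All of these sizes rest on the assumed core SDs, error rates and error sizes, and on the unstated pairing interval. Whether the interval affects the pass decision is also unstated. If only the point limits count, the interval problem affects reporting and not the verdict.

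**What to change.** In the Limits of Agreement paragraph, for FHR and MHR alike:

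1. Keep mean ± 1.96 SD as the primary limits compared with ±10 and ±7 bpm, and compute their 95% confidence intervals by a bootstrap that resamples whole women.
2. Add, as a prespecified sensitivity analysis, the 2.5th and 97.5th percentiles of the differences with the same bootstrap intervals, the share of pairs outside the margin, and the share beyond a large-error cut-off fixed now (for example 25 bpm).
3. State the pairing interval before pivotal data are analysed.

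The cost is some plan wording, a little more analysis work and probably wider reported intervals. If the differences turn out normal, the percentile limits are less precise: their standard error is [√(0.025 × 0.975)/φ(1.96)]/√2.921 = 2.67/1.71 = 1.56 times that of mean ± 1.96 SD. This matters little in a supporting analysis. The bootstrap cannot recover errors absent from the sample. With one value per woman and a 1% error rate, 0.99^60 = 55% of trials would contain no error at all.

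### Across the heart-rate range the plan checks only whether the bias is constant, not the spread, so pooled limits close to ±10 and ±7 bpm could pass while agreement at high rates is wider

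*Combined protocol and SAP*

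**What the plan says.** The Clinical Investigation Plan Summary treats this point in two rows.

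- **Endpoints.** The primary endpoints are "95% LoA for FHR within +/- 10 bpm" and "95% LoA for MHR within +/- 7 bpm". A regression of MFM-Pro against CTG for both parameters is listed with them, for the purpose of "determining if the bias is constant across the range of the measurements".
- **Statistical Data Analysis.** Limits are to be estimated by the Bland-Altman method with 95% confidence intervals. The objectives repeat the same two figures. The regression is described once more: "A linear regression analysis assessing the relationship between the bias and the magnitude of measurements will also be performed".

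Neither row mentions a check that the standard deviation of the differences is constant, a regression of absolute residuals, rate-dependent limits, limits by heart-rate band, or a log or ratio scale. No expected standard deviation or bias is given. The sample size is a cap with no derivation: "Pivotal phase: up to 60 enrolled subjects".

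**The concern.** A single pair of limits describes agreement over the whole range only if two things hold: the mean difference does not depend on heart rate, and neither does the standard deviation of the differences. The sponsor saw the need for a check across the range and placed it among the primary endpoints, but it covers only the first condition. A regression of the differences on magnitude looks at their mean. If the differences fan out symmetrically around that mean, the slope need not move.

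There is a plausible reason why spread might grow. The investigational device takes its rates from electrocardiographic signals, and rate is the reciprocal of the beat interval, so a fixed timing error becomes larger in bpm as the rate rises. Most readings lie near the middle of the range and dominate a pooled standard deviation. The study could then report equivalence and a constant bias while agreement at fast fetal or maternal rates was clearly poorer than the stated figures suggest.

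**Working it through.** The plan gives no standard deviation, power or derivation, so there is no figure of its own to reproduce.

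**Inputs from the documents:** limits of ±10 bpm (fetal) and ±7 bpm (maternal), up to 60 pivotal subjects, 45 minutes of paired recording each.

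**Assumptions, not in the documents:** the distribution of rates, the averaging interval and every variance pattern below.

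**1. Room available.** With zero bias the limits are ±1.96 × SD. The largest passing pooled SD is 10/1.96 = 5.10 bpm (fetal) and 7/1.96 = 3.57 bpm (maternal).

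**2. Two-zone arithmetic, zero bias throughout, 10% of pairs at high rates.**
- Fetal, SD 4.0 in the lower zone and 7.0 in the upper: pooled 1.96 × √(0.9 × 4.0² + 0.1 × 7.0²) = ±8.6 (pass). Upper zone: 1.96 × 7.0 = ±13.7, with 15% of its differences beyond 10 bpm.
- Maternal, SD 2.8 and 5.0: pooled 1.96 × √(0.9 × 2.8² + 0.1 × 5.0²) = ±6.1 (pass). Upper zone: 1.96 × 5.0 = ±9.8, with 16% beyond 7 bpm.

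**3. Constant beat-interval error.** Since HR = 60000/interval (ms), an interval error of d ms becomes about d × HR²/60000 bpm. The growth is (160/110)² = 2.1 from 110 to 160 bpm and (110/60)² = 3.4 from 60 to 110 bpm. The simulation used 60 women with 2700 one-second pairs each and equal error in both devices. Fetal means were N(140, 10) with within-woman SD 8; maternal means were N(85, 11) with within-woman SD 5.

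| Parameter | Pooled limits (bpm) | Limits in the high band (bpm) |
|---|---|---|
| Fetal, 155–170 bpm | ±9.8 | about ±12.4 |
| | ±8.0 | about ±10.2 |
| | ±7.0 | about ±8.9 |
| Maternal, 100 bpm or more | ±6.9 | about ±10.1 |
| | ±5.5 | about ±8.1 |
| | ±4.5 | about ±6.6 |

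Repeat runs differ by a few tenths of a bpm. The mean bias slope was 0.000 for both parameters. The ratio of band to pooled limits is roughly 1.27 (10.2/8.0) for fetal and 1.47 (8.1/5.5) for maternal. Under this model the band therefore exceeds its criterion once pooled limits pass about 10/1.27 = 7.9 or 7/1.47 = 4.8 bpm.

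**4. Two other variance models** (mean rates 140 and 85, SD of rates 12 bpm).
- SD linear in rate, SD(x) = s₀[1 + g(x − mean)/12], pooled variance s₀²(1 + g²), pooled limits at 90% of the criterion. If SD at mean + 2 SD of rate is 1.5 times that at the mean, g = 0.25. At 160 bpm, 9.0 × (1 + 0.25 × 20/12)/√1.0625 = ±12.4. At a maternal rate of 105 bpm, the same factor times 6.3 gives ±8.7. With a ratio of 1.25 the figures are ±10.8 and ±7.6.
- SD proportional to rate. The root-mean-square fetal rate is √(140² + 12²) = 140.5. Pooled ±9.0 gives 9.0 × 160/140.5 = ±10.25 at 160 bpm. Pooled ±8.0 gives ±9.1 at 160 and ±10.25 at 180 bpm.

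**5. What each test detects.** This simulation used 60 women with 45 one-minute pairs each, 400 runs per scenario, pooled limits at 90% of the criterion, independent differences and tests clustered by woman. With SD ratios of 1.5, 2 and 3, the bias-slope test was significant in 5.5–8% of runs, close to its nominal 5%. A regression of absolute residuals was significant in 100% of them, and in 4.5% of runs with constant spread. At ratio 1.5, pooled limits including their confidence intervals passed with no significant bias slope in 93.5% (fetal) and 91.5% (maternal) of runs. Limits in the top tenth of rates averaged ±12.5 and ±8.8.

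**The case against.** **The pooled criterion is not shown to be wrong.** The plan sets no rate-specific criterion. In the near-boundary scenario of step 3, about 95% of pairs still fall within ±10 (fetal) and ±7 bpm (maternal). This stands: the pooled limits remain a fair overall summary, and the gap lies in what is reported beside them.

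**The size depends on slack.** Pooled fetal limits of ±7.0 or maternal limits of ±4.5 leave the high bands inside the criterion. If the confidence intervals also had to lie inside it, which the plan does not say, and the effective sample were only 60 independent differences, the largest passing pooled SD would be 10/[1.96 + 1.96 × √(1/60 + 1.96²/118)] = 4.18. That means pooled limits of ±8.2 (fetal) and, by the same formula, ±5.7 (maternal). The step 3 ratios then give about 8.2 × 1.27 = ±10.4 and 5.7 × 1.47 = ±8.4 in the high bands. The fetal excess nearly disappears and the maternal one shrinks.

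**A zero slope needs equal error in both devices.** Nothing in the documents says the errors are equal. If one device has half the other's error, slopes of about 0.05 (fetal) and 0.03 (maternal) bpm per bpm appear. This also stands, although such a slope would not identify changing spread as its cause.

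**The error law is assumed.** Averaging, dropout and misdetection need not follow a square law, and step 4 gives smaller excesses under proportional spread.

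**A check may be implied or exist elsewhere.** Bland-Altman analysis often includes a plot of differences against magnitude, and the document is a summary. That may be so, but the supplied text writes no such check and ties no consequence to one.

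**Conclusion.** The gap is real and conditional. The plan checks one of the two conditions that a single pair of limits relies on, and the check it has cannot stand in for the other. If spread rises with rate and the pooled limits come close to the criterion, limits at high rates could exceed it by about 2.4 bpm for fetal (12.4 − 10) and 3.1 bpm for maternal heart rate (10.1 − 7) in the near-boundary case of step 3. The excess falls to nothing as slack increases.

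A reader might go further and infer that this device's spread does rise with rate, that it fails at high rates, or that the pooled criterion is invalid. The documents support none of these. They contain no data on spread, no averaging interval and no rate-specific requirement. Nor can it be said that the planned regression would always be flat, since that rests on equal error in the two devices.

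The addition should be made. Confidence is medium, because the size rests on an assumed variance pattern and on where the pooled limits will fall.

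**What to change.** Keep the pooled limits against ±10 and ±7 bpm as the primary pass/fail criterion. Add to Statistical Data Analysis, for each parameter:

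- A regression of the absolute residuals from the bias regression on the pair mean, with standard errors clustered by woman.
- Limits as a function of rate, fitted bias ± 2.46 × fitted absolute residual (2.46 = 1.96 × √(π/2)), or limits in heart-rate bands fixed before the data are seen. Either should carry 95% confidence intervals clustered by woman and be set against ±10 and ±7 bpm.
- Empirical percentiles in place of the 2.46 multiplier if residuals are clearly non-normal, because the multiplier assumes normality.
- A rule that the conclusion states any part of the observed range where these limits exceed the criterion.

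The equivalence claim should not be restricted to whichever range turns out to pass. That would turn a pass/fail criterion into one selected from the data.

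The cost is a few lines of text and one extra regression per parameter on data already collected. Limits in the sparse upper range will be imprecise and may rest on few women, and the equivalence statement may have to be qualified.
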